9.2.4. Exploratory Analysis - Comparison with the CINRG natural history data

Efficacy endpoints: % predicted FCV (ppFVC), LVEF, and grip strength in dominant hand will be compared with a subset of CINRG DMD Natural History study (DNHS) data with all 36 subjects using a random coefficient model (RCM). The other outcome measures including Performance of Upper Limb (PUL), cardiac fibrosis by LGE, and Myocardial Circumferential Strain [Mean Peak Circumferential strain (MPCS) and Global Circumferential Strain (GCS) percentage] assessed by cardiac MRI are not available in CINRG data and therefore will not be compared.. The RCM model will use efficacy data from both the main and OLE periods and include continuous variable avisityr (calculated as the elapsed days of assessment date from main study baseline date in the unit of year), treatment trt (079 subjects as treated with trt = 1, and subjects in CINRG data as control with trt =0), the interaction term of trt and avisityr, and baseline endpoint as fixed effects, while the intercept and avisityr are included as random effects. The strategy for covariance structure for the within-patient errors in the model is the same as what is described in [Section 9.2.2.1](#). The LSMean (SE) for annual change (slope) as well as LSMean (SE) and 95% CI of treatment differences between pamrevlumab and control of estimated changes from baseline at year 1, year 2, year 3 and year 4 in the OLE period will be presented. The sample SAS code is provided in [Appendix 2](#).

Line plots of each subject's efficacy trajectory compared with the mean plot of the CINRG will be provided.

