#### **4.2. Trial Overview**

This study will be an open-label, single arm study that will initially enroll approximately 22 subjects and includes an open label extension (OLE). Each subject will receive pamrevlumab (35 mg/kg, every 2 weeks) for a minimum of 104 weeks and will transition onto the OLE within 2-3 infusions from the approval of the amendment. An interim analysis will be conducted after at least 10 to 12 subjects have completed 1 year of treatment. As a result, sample size may be readjusted to a total of approximately 32 subjects.

All subjects will be closely monitored for safety (including trends of pulmonary function tests: FVC, mean inspiratory flow, and peak expiratory flow) on a continuous basis.

Upon completion of treatment or premature discontinuation from the trial, subjects will be asked to return to the investigative site to complete final safety and efficacy assessments.

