## Pamrevlumab

## Protocol FGCL-3019-079 Amendment 8

- d. Weight and height (estimated from ulna length) to be measured in screening and approximately every 3 months thereafter.
- e. Physical exam to include assessment of subject's ventilation use. A complete exam is required at Week 208/EOT. Other exams may be disease specific or problem oriented.
- f. Muscle function tests: Brooke Scale, Performance of Upper Limb, Pinch Strength Test, and Grip Test.
- g. Pulmonary Function Tests (PFTs): forced vital capacity, forced expiratory volume in 1 second, maximal inspiratory pressure, maximum expiratory pressure, peak expiratory flow rate, peak cough flow.
- h. See [Section 5](#) for pharmacokinetic/human antihuman antibody/connective tissue growth factor and Exploratory Sample collection details.
- i. Local safety labs required prior to the MRIs and must include hematocrit.
- j. Pamrevlumab infusion is administered at Week 156, but is NOT to be administered at week 208/EOT.

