## 6. OLE Schedule of Assessments: EX – Day 0 through Ex – week 210/EOS/ET

	Treatment Period a					Follow Up Period	
	Day 0 b	Q2 WEEKS: ALL VISITS through Week 206	Q12 weeks through Week 204 (Wk 12, 24, 36, etc.)	Q24 Weeks (Wk 24, 48, 72, etc.)	Q52 weeks through Week 156 (Wk 52, 104, 156, 208 r /EOT)	Wk 210/ EOS/ET p	Final Safety phone call 60 Days (+3 days) after last treatment
Informed Consent & Assent	x						
Eligibility Assessment	x						
Vital Signs c	x	x	x	x	x	x	
Chemistry & Hematology				x		x	
PFT / Height (ulna length) f,h,i				x		x q	
Muscle Function Tests f,g			x	x		x q	
Physical Examination k				x		x	
Weight j	x		x	x			
Weight Based Dose Adjustment j	x		x	x			
Cardiac MRI d,e,f					x	x q	
Specialty Labs o	x					x	
Pamrevlumab Infusion l	x	x	x	x	x		
AEs / SAEs m	x	x	x	x	x	x	x
Concomitant Medications n	x	x	x	x	x	x	x

Abbreviations: AE = adverse event; ECG = electrocardiogram; ET= Early Termination; ICF = Informed Consent Form; PFTs = Pulmonary Function Test;

a.) Visit window of  $\pm$  3 days starting at Week 2.

b.) Day 0 to be conducted simultaneously with, or within 7 days after the parent study EOT visit.

c.) Vital signs (pulse, respiration, sitting BP, temperature) to be collected at every visit: pre-infusion, and within 15 minutes of completion, and within 15 minutes of completing the observation period.

d.) Local safety labs are required prior to MRIs and must include hematocrit.

e.) Cardiac MRI may be performed within  $\pm$ 2 weeks of the specified visit

f.) PFTs, MFTs, and MRI do not require repetition if performed within 4 weeks.

- g.) For Non-ambulatory subjects only: Muscle Function Tests (MFTs): Performance of Upper Limb, and Grip Test.
- h.) Pulmonary Function Tests (PFTs): forced vital capacity, forced expiratory volume in 1 second, peak expiratory flow rate.
- i.) Height will be measured at each PFT interval using ulna length to approximate standing height until subject reaches adult height. Adult height will be carried forward.
- j.) Weight will be measured every 12 weeks to determine dose for the subsequent 12-week interval. Weight is collected during the dose adjustment visit or up to two weeks in advance.
- k.) Full physical exam including chest auscultation

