2. STUDY DESIGN

This study is designed as the open-label extension (OLE) of the main study FGCL-3019-079. All subjects participating in the OLE must have completed treatment through the primary endpoint and completed the End of Treatment (EOT) visit of the main study FGCL-3019-079.

Each subject in the OLE receives pamrevlumab (35 mg/kg, every 2 weeks) for up to 208 weeks. The dosing period began on the first day of dosing with study treatment (Day 1) in the OLE, which is to be conducted simultaneously with, or within 7 days after the parent study EOT visit. The dosing period continued until Week 208/EOT.

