3. STUDY OBJECTIVES

3.1. Primary Objective

The primary objective of this trial is to evaluate long-term efficacy and safety of pamrevlumab in non-ambulatory DMD subjects who have been previously treated with pamrevlumab for a minimum of 104 weeks.

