APPENDIX 2. SAMPLE SAS CODE FOR RCM ANALYSIS

SAS code for this model, using the primary endpoint ppFVC as example, is provided below.

```

/*Random Coefficient Model (RCM) to estimate the change at year 1, 2, 3 and
4*/
/*avisityr is the actual number of years from Day 1, avisityr=4 will be
the change from baseline at year 4 */
/* fvc0= baseline ppFVC, should be used for change in FVC */
/* &meanfvc0= the mean of the baseline ppFVC           */

proc mixed data = fvc_obs;
  class subjid;
  model chgfvc = avisityr fvc0/solution cl covb outp=pred_fvc cl;
  random intercept avisityr /subject=subjid type=CS;
  ESTIMATE 'Change from Baseline at Year 1' intercept 1 avisityr 1 fvc0
  &meanfvc0 / CL;
  ESTIMATE 'Change from Baseline at Year 2' intercept 1 avisityr 2 fvc0
  &meanfvc0 / CL;
  ESTIMATE 'Change from Baseline at Year 3' intercept 1 avisityr 3 fvc0
  &meanfvc0 / CL;
  ESTIMATE 'Change from Baseline at Year 4' intercept 1 avisityr 4 fvc0
  &meanfvc0 / CL;
  ods output SolutionF=mxparms CovB=mxcovb Estimates=chgfrbl;
run;

```

Sample SAS code for comparison 079 OLE data (trt = 1) with CINRG (trt = 0).

```

PROC MIXED DATA = final;
  CLASS trt SUBJID ;
  MODEL chg = trt|avisityr base/ SOLUTION DDFM=KR;
  RANDOM intercept avisityr / SUBJECT =SUBJID TYPE=UN GROUP= trt;

  LSMEANS trt/ at avisityr = 1 PDIFF CL;
  LSMEANS trt/ at avisityr = 2 PDIFF CL;
  LSMEANS trt/ at avisityr = 3 PDIFF CL;
  LSMEANS trt/ at avisityr = 4 PDIFF CL;

  ods output LSMeans=LSMeans_chg diffss=diffs_chg;
RUN;

```

Statistical Analysis Plan

Addendum

TITLE PAGE

PROTOCOL TITLE: A Trial of FG-3019, a Monoclonal Antibody to Connective Tissue Growth Factor, in Non-Ambulatory Subjects with Duchenne Muscular Dystrophy (DMD)

PROTOCOL NUMBER: Protocol FGCL-3019-079

STUDY SPONSOR: FibroGen, Inc.
[name]
[name]

STUDY DRUG: Pamrevlumab

INDICATION: Duchenne Muscular Dystrophy (DMD)

SAP VERSION Addendum v1.1

RELEASE DATE August 08, 2023

[figure not shown]
CONFIDENTIALITY STATEMENT

The information contained in this document is confidential and proprietary to FibroGen, Inc. No part of this document or any of the information contained herein may be transmitted, disclosed, shared, reproduced, published or utilized by any persons without prior written authorization by FibroGen, Inc.

SIGNATURES AND APPROVALS**Approvals**

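### The CINRG comparison fits one straight line per group with no common follow-up period, so the slope and later-year differences lean toward pamrevlumab if controls were followed for less time and decline slows late.

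*SAP*

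**What the plan says.** SAP 9.2.4 compares ppFVC, LVEF and dominant-hand grip strength with 36 CINRG subjects. On the data it says: "The RCM model will use efficacy data from both the main and OLE periods". The time variable, avisityr, is "calculated as the elapsed days of assessment date from main study baseline date in the unit of year". The fixed effects are treatment, time, their interaction and baseline; intercept and time are also random. There is no curvature term.

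The outputs are an annual slope and group differences at years 1, 2, 3 and 4. The code in SAP Appendix 2 reads the differences at avisityr 1 to 4, the last line being "LSMEANS trt/ at avisityr = 4 PDIFF CL". It contains no restriction on time. The text of 9.2.4 places these four years within the extension period, although avisityr counts from main-study baseline.

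On follow-up:
- Protocol 4.2: "Each subject will receive pamrevlumab (35 mg/kg, every 2 weeks) for a minimum of 104 weeks". SAP 3.1 likewise describes subjects as "previously treated with pamrevlumab for a minimum of 104 weeks".
- The main-study schedule continues to Week 208. The footnote in Protocol Appendix 4 reads: "Pamrevlumab infusion is administered at Week 156, but is NOT to be administered at week 208/EOT".
- SAP 2: "Each subject in the OLE receives pamrevlumab (35 mg/kg, every 2 weeks) for up to 208 weeks".
- In the extension, pulmonary function tests fall under "Q24 Weeks (Wk 24, 48, 72, etc" (Protocol Appendix 6, Section 6). The last PFT analysis visit in SAP Appendix 1 is Week 192, with no upper bound.

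Neither document gives the length or visit spacing of CINRG follow-up.

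**The concern.** When the true course is curved, the slope of a fitted straight line depends on how long subjects are followed. Two groups on an identical curve but with different follow-up then get different slopes and intercepts, and the model reports that gap as a treatment difference. The baseline covariate does not remove it, because the gap appears even when baselines are equal. Trial data from after year 4 also shape the values fitted at years 1 to 4.

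This is the external comparison that 9.2.4 specifies for a single-arm trial; adjusted or matched analyses are left to a separate SAP if warranted (SAP 9.2). SAP 9.1 adds a mixed model for repeated measures precisely so as not to assume linear trajectories, but that model is single-arm. The between-group comparison has no such safeguard.

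**Working it through.** **The plan's own figure.** No size or power is given for this comparison. The only sizing figure is the main study's 22 subjects (Protocol 9.1: -2 against -5, SD 5). The normal approximation reproduces it: ((1.960 + 0.842) × 5/3)² = 21.8, rounded up to 22. It is used here only for scale: the trial was sized on a difference of 3 points.

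**Follow-up from main-study baseline** (52-week years)
- Treatment span: 104 + 208 = 312 weeks (6.0 years) to 208 + 208 = 416 weeks (8.0 years).
- Last scheduled ppFVC: 104 + 192 = 296 weeks (5.7 years) to 208 + 192 = 400 weeks (7.7 years).

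**Spurious difference with no drug effect**
- From the documents: trial PFT visits at main-study Weeks 12, 24, 36, 48, 60, 72, 84 and 104; for the longer case also 116, 128, 140, 156, 168, 180, 192 and 208; then every 24 weeks to extension Week 192.
- Assumed: the same curve in both groups, ppFVC = 65·exp(-0.08t), and half-yearly control visits for 2, 3 or 4 years.

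Fit a line a + bt to the change from baseline in each group. The spurious difference at year t is D(t) = (a_trial - a_control) + (b_trial - b_control)·t. With common visit times within a group, generalised least squares with a random intercept and slope gives the same mean line as ordinary least squares, so the result does not depend on assumed variances.

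Fitted slopes are -4.15 (104-week main study) and -3.86 (208-week) for the trial. For controls they are -4.71, -4.53 and -4.35 with 2, 3 and 4 years. The differences below are rounded from unrounded slopes.

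| Main study | Control follow-up | Slope/yr | Year 1 | Year 2 | Year 3 | Year 4 |
|---|---|---|---|---|---|---|
| 104 wk | 2 y | +0.55 | -0.11 | +0.45 | +1.00 | +1.55 |
| 104 wk | 3 y | +0.37 | -0.09 | +0.28 | +0.65 | +1.03 |
| 104 wk | 4 y | +0.20 | -0.02 | +0.18 | +0.38 | +0.58 |
| 208 wk | 2 y | +0.84 | -0.51 | +0.34 | +1.18 | +2.03 |
| 208 wk | 3 y | +0.66 | -0.49 | +0.17 | +0.84 | +1.50 |
| 208 wk | 4 y | +0.49 | -0.42 | +0.07 | +0.56 | +1.05 |

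Cutting the trial data to the control follow-up leaves a slope difference of -0.05 to -0.09 per year, and no difference at years 1 to 4 above 0.17 points in size. The small remainder comes from unequal visit spacing.

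**Why year 1 goes the other way.** Each group has its own intercept, so the longer-followed line is flatter but starts lower. In the 208-week, 2-year case it starts 1.35 points lower (-0.51 - 0.84). For a quadratic curve with evenly spread visits over T1 and T0 years, the sign changes at (T1 + T0)/6: from (5.7 + 2)/6 = 1.3 years to (7.7 + 4)/6 = 2.0 years.

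**Other assumed shapes** (initial decline 5 points per year, controls 2 to 4 years)
- Smooth slowing, -5t + 0.25t²: slope +0.31 to +1.29; year 1 -0.04 to -0.82; year 4 +0.89 to +3.06.
- Slowing to 2 points per year after year 4: slope +0.68 to +1.38; year 4 +1.72 to +2.89.
- Linear: zero throughout.
- Speeding up to 8 points per year after year 4: slope -0.68 to -1.38; year 4 -1.72 to -2.89.

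**The case against.** The strongest reply is that both conditions for the bias are assumed. CINRG follow-up is not stated and may match the trial's. No passage shows that decline slows: Protocol 2.2 cites a median loss in ppFVC of 8.0% per year without saying whether it is proportional. Read as percentage points, decline is linear and the bias is zero. This stands. It makes the size and direction unknown, but it does not protect the analysis, because the plan neither checks linearity in this comparison nor reports how follow-up differs.

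A reader might infer that any late flattening is credited to pamrevlumab. The documents do not support that. At year 1 the bias runs against the drug in every case above, and late acceleration reverses the signs. A reader might also infer that years 1 to 4 are the only output, but a slope is reported too.

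A third reply is that the SAP's purpose is long-term efficacy, analysed through the last extension visit, so truncation discards what the extension was run to collect. A cut at 4 years keeps about two extension years after a 104-week main study and almost none after a 208-week one. This stands against replacing the all-data fit, though not against adding a restricted one.

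Finally, the comparison is exploratory, 208 extension weeks is an estimated maximum (Protocol Appendix 6, note r), and individual trajectories will be plotted against the CINRG mean. The plots could reveal curvature but do not correct the estimates. The effect is also modest against sampling error: in a simulation of 20 trial subjects and 36 controls followed 6 and 4 years, a slope bias of about 0.3 compares with an SD of 0.51 for the slope difference, a ratio of about 0.6.

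**Conclusion.** The concern holds conditionally. The documents establish one straight line per group, all main-study and extension data, differences read at avisityr 1 to 4, and neither a common follow-up period nor a curvature check. If controls were followed for 2 to 4 years and ppFVC falls by 8% per year proportionally from 65, the comparison shows about +0.2 to +0.8 points per year in slope and +0.6 to +2.0 points at year 4 with no drug effect. At year 1 it shows -0.02 to -0.51, against the drug. The year-4 figure can be a sizeable fraction of the 3-point annual difference on which the trial was sized, although it accrues over four years.

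The documents do not show that the comparison is in fact biased toward pamrevlumab, since control follow-up and the shape of decline are both unknown. Only ppFVC was sized; LVEF and grip strength use the same model.

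Separately, the text and the time variable disagree on which years are meant. Year 4 of the extension would be avisityr of about 6 to 8, whereas the code reads avisityr 4. This needs settling, because it decides whether the late data are the target or only influence the estimates.

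**What to change.** In SAP 9.2.4:

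1. Report the distribution of follow-up and visit timing in both groups.
2. Add a pre-specified random coefficient comparison restricted, in both groups, to the follow-up they share. Fix the cut-off rule in advance on the bulk of CINRG follow-up, for example the time by which a stated share of controls still contribute data. Do not use the single longest control: if most controls stop at 2 years and trial data run to 4, the same curve with half-yearly visits still gives a slope bias of about +0.35 per year.
3. Present the restricted fit beside the all-data fit. If they disagree, by a criterion stated in advance, base the year 1 to 4 differences on the restricted fit as far as the shared period reaches.
4. Do not describe differences beyond the shared period as supported by control data.
5. Reconcile the wording on extension years with avisityr counted from main-study baseline, in both the text and Appendix 2.

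The cost is a short paragraph, one WHERE clause and some precision. In the 6 v 4-year simulation the SD of the slope difference rose from 0.51 to 0.60 (0.60/0.51 = 1.18, about 18%), and that of the year-4 difference by about 8%. No data are lost, because the all-data fit remains. If decline is linear, the two fits should agree apart from sampling error.

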9.2. Analysis Methods for Efficacy Endpoints

Unless otherwise noted, long-term treatment effects of all efficacy endpoints at each timepoint will be summarized and analyzed from the baseline of the main study through the last visit in the extension phase. Change from baseline values in efficacy endpoints will be analyzed with MMRM Annual rate of change from baseline using Random Coefficient Model (RCM) analysis, and the estimated change from baseline values at year 1 through year 4 described in the following sub-sections will be presented.

The sponsor will conduct an exploratory comparison of disease progression of FGCL-3019-079 clinical trial participants with natural history data of patients with non-ambulatory DMD. If

warranted, analyses adjusting for matching on established baseline prognostic factors will be conducted under a separate SAP.

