9.2.3.1. Analysis Method

The observed and change from baseline in the above efficacy endpoints each will be summarized by analysis visit and analyzed using MMRM with visit, baseline, and age with appropriate covariance matrix for the within subject covariance over time.

If the algorithm for unstructured covariance pattern does not converge, the following covariance structures will be tested in sequence until the model converges: heterogeneous Toeplitz, homogeneous Toeplitz, first-order autoregressive, compound symmetry, and variance component. The sandwich estimator will be used if there is convergence issue. If the model does not converge for all covariance structures listed above, some least significant factors or interaction terms ($p>0.05$) can be excluded from the model to achieve convergence. The revised model with fewer factors or interaction terms will be tested using the same sequence as specified above.

9.2.3.2. Handling of Intercurrent Events:

Treatment discontinuation (such as: due to AEs, Lost to Follow-Up, Withdrawal by subject, Physician Decision, Protocol Deviations, etc.): treatment policy: the occurrence of the intercurrent event is irrelevant. All observed values will be used regardless of whether the inter-current event occurs.

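### The CINRG slope comparison has baseline as a main effect only and no age, so any group difference in either that predicts rate of decline passes in full into the slope contrast

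*SAP*

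**What the plan says.** SAP 9.2.4 compares ppFVC, LVEF and dominant-hand grip strength with "a subset of CINRG DMD Natural History study (DNHS) data with all 36 subjects". The 36 are read here as the controls. No rule for choosing the subset is given.

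The fixed effects are time since main-study baseline (`avisityr`), treatment, "the interaction term of trt and avisityr, and baseline endpoint as fixed effects". The code in SAP Appendix 2 agrees: "MODEL chg = trt|avisityr base/ SOLUTION DDFM=KR", with "RANDOM intercept avisityr / SUBJECT =SUBJID TYPE=UN GROUP= trt". The outputs are "The LSMean (SE) for annual change (slope) as well as LSMean (SE) and 95% CI of treatment differences between pamrevlumab and control" in estimated change at years 1 to 4.

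Two other places bear on this. The within-trial model in SAP 9.2.3.1 is "analyzed using MMRM with visit, baseline, and age with appropriate covariance matrix", so age is used there. SAP 9.2 calls the CINRG comparison exploratory and adds that, if warranted, "analyses adjusting for matching on established baseline prognostic factors will be conducted under a separate SAP". It sets no trigger and names no factors.

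**The concern.** The quantity of interest is a difference in rate. Having baseline in the model looks like control for baseline differences. But a term that is not crossed with time can only move the intercept of the change score. It cannot account for one group declining faster because it started from a different value, and nothing in the model accounts for age.

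The trial group was selected: protocol 5.1 requires age 12 or over, non-ambulatory status, ppFVC 40 to 90, LVEF of at least 45% and stable corticosteroids. Protocol 2.2 ties the onset of respiratory loss to age. A group difference in a slope predictor is therefore plausible. If one exists, an inactive drug could appear to slow decline, or an active one could appear not to.

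**Working it through.** **No figure to reproduce.** The documents give no sample size, power or target difference for this comparison, so the check is algebra plus simulation.

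**Algebra.** Let a subject's true slope be a + b·X, where X is baseline or age. With X absent, or present only as a main effect, the fitted `trt*avisityr` has expectation

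true effect + b × (mean X in trial − mean X in controls).

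Random slopes, group-specific covariance and Kenward-Roger degrees of freedom affect the variance. They do not remove a systematic group difference.

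**Inputs.** From the documents: the model terms and 36 controls (SAP 9.2.4, Appendix 2), two-sided 5% tests (SAP 5.1), and the planning difference of −2 against −5, or 3 points (protocol 9.1). All else is assumed: 20 trial subjects, 4 years, mean slope −5/yr, slope SD 2, measurement SD 4, baseline SD 12, age SD 2.5, trial visits every 6 months, CINRG visits annual, no drug effect. The fit was GLS with known variance components, 600 runs per scenario.

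| Assumed imbalance and b | b × difference | Simulated slope bias (/yr) | False positives (slope) | Year-4 bias |
|---|---|---|---|---|
| None | 0 | 0.01 | 5% | – |
| Baseline 10 points, b = 0.05/yr per point | 0.5 | 0.48 | 11% | 2.5 |
| Baseline 10 points, b = 0.10/yr per point | 1.0 | 1.01 | 32% | 4.2 |
| Age 2 years, b = 0.3/yr per year | 0.6 | 0.60 | 15% | 2.3 |
| Age 2 years, b = 0.5/yr per year | 1.0 | 1.00 | 34% | 3.9 |

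Across repeats the slope bias ran from 0.47 to 1.01/yr. A second simulation (REML, 21 treated, residual SD 3, 150 replicates, Wald tests, some convergence warnings) gave +0.99 and +1.05/yr with 33% rejections for the two b × difference = 1.0 cases. With balanced groups it gave 0.04/yr and 3% rejections. The sign reverses if the imbalance or the slope relation reverses.

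**Scale.** The protocol's endpoint is annual change, so its 3 points are per year. The like-for-like ratio is 0.5/3 = 17% to 1.0/3 = 33%.

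**After adding baseline-by-time and age-by-time.** Slope bias falls to about 0.1/yr or less, and false positives to 3 to 6%. Age as a main effect alone leaves the slope contrast unchanged (0.991 and 1.054 in the REML runs).

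**What the added terms leave behind.** Measured baseline contains error. If 12 is the SD of true values, the error share is 16/(144 + 16) = 0.10. With a 10-point imbalance this gives:
- a level bias of 0.10 × 10 = 1.0 point, even with no baseline-slope relation (simulated: about 0.9);
- a residual slope bias of 0.10 × 0.5 = 0.05/yr or 0.10 × 1.0 = 0.10/yr;
- a year-4 bias of 1.0 + 4 × 0.05 = 1.2 or 1.0 + 4 × 0.10 = 1.4, in line with the simulated 1.0 to 1.4.

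**Precision.** In the age scenarios the SD of the slope difference rose from 0.68–0.74 to 0.78 (5 to 15%). In a harder case (age-baseline correlation −0.6, trial 10 points higher and 2 years older, slope related to baseline only) it rose from 0.70 to 0.93 (33%), and year-4 bias did not improve (2.7 to 2.9). With the age imbalance reversed, the SD went from 0.72 to 0.78 and year-4 bias fell from 2.4 to 0.5.

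**The case against.** **The imbalance is assumed.** This stands. The documents hold no CINRG ages, baselines or selection rule; these may be in the main-study SAP, which is not provided. A reader might infer that the comparison is biased in the drug's favour. The documents support neither the direction nor the existence of an imbalance, only that the model has no protection against one.

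**The year-4 biases of 2.3 to 4.2 look as large as the 3-point planning effect.** That reading mixes scales: 3 points per year is about 12 points by year 4. In the baseline scenarios part of the year-4 figure also comes from measurement error in baseline, not from the missing interaction.

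**SAP 9.2 already foresees adjustment.** It is conditional, names no trigger or factors, and is deferred to another document. It softens the point but leaves the model in 9.2.4 as it is.

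**The MMRM is weak precedent.** Agreed: it is a single-arm model with age as a main effect, and the within-trial random coefficient model in SAP 9.2.2.1 also omits age. The argument here rests on the algebra, not on consistency with the MMRM.

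**It is exploratory.** True, and it limits the severity. It still yields 95% confidence intervals for three endpoints.

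**Conclusion.** The point holds as a conditional one. As specified in text and code, the CINRG model offers no protection for its slope contrast against group differences in baseline or age that predict rate of decline. That part rests on algebra and is firm. The size is illustrative: about 0.5 to 1.0 points/yr and 11 to 34% false positives for the slope, given a 10-point or 2-year imbalance and the slope relations in the table. The false-positive rates apply to the slope test, not to the year-specific differences. Only ppFVC-like data were simulated, not LVEF or grip strength.

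Two stronger statements are not supported. One is that this is the trial's only between-group efficacy evidence. It is the only such comparison in the OLE SAP, but section 2 of the SAP addendum corrects a two-sample test from the main-study SAP. The other is that the added terms would make the comparison unbiased. They deal with two measured factors, largely for the slope. Year-4 bias of about 1.0 to 1.4 points remains with a 10-point baseline imbalance, and up to about 3 when age and baseline are correlated and both imbalanced.

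**What to change.** In SAP 9.2.4 and Appendix 2, use `MODEL chg = trt|avisityr base|avisityr age|avisityr`. Evaluate LSMEANS, with AT, at subject-level means of `base` and `age`. Keep the current model as a sensitivity analysis.

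Define age the same way in both groups, at the main-study baseline for trial subjects and at the index visit for CINRG controls. SAP 7.1 now defines it only as consent year minus birth year and says nothing for controls. Availability of age for controls is an assumption.

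In the text, state that residual confounding and baseline measurement error remain, the latter affecting the year 1 to 4 differences in particular.

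Cost: a line of code, a sentence on the model and an age definition. The SD of the slope difference usually changes by 15% or less, but can rise by about 25 to 33% when age and baseline are correlated and both imbalanced.
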